3.8.1 Schedule of Assessments

The investigator or subinvestigator will perform observations, tests, and assessments within the allowable windows shown in Table 3.8-2 according to the schedule of assessments shown in Table 3.8-1. Special consideration should be given to environmental factors (eg, physical restraint [including isolation] and transfer to a different ward or room, staying out overnight, and outings during hospitalization/institutionalization) that may affect assessments. The investigation of subject background information, clinical laboratory tests, and other investigation/test items that can be performed by the trial collaborator may be performed by the trial collaborator under supervision of the investigator.

The methods employed for observations, tests, and assessments are shown in Section 3.8.2 Efficacy Assessments to Section 3.8.5 Other Endpoints.

The date and time of observations, tests, and assessments and the results will be recorded in the source document and case report form (CRF).

3.8.1.1 Screening Period

To confirm that the subject meets the inclusion criteria and does not fall under the exclusion criteria, observations, tests, and assessments will be performed, and the results will be recorded after the date of informed consent but before the baseline assessment.

The caregivers will be provided with the subject diary for the period up to the baseline evaluation and be given an explanation on how to complete the subject diary, and instructed to record the required information in the subject diary from 14 days before the baseline evaluation until the baseline evaluation. In the subject diary, occurrence of daily symptoms will be recorded to evaluate the frequency of occurrence of agitation associated with dementia of the Alzheimer's type (CMAI).

The investigator or subinvestigator will record subject information related to the enrollment criteria, which had been collected during screening, in the eligibility form specified by the sponsor and submit to the medical monitor for confirmation of the subject's eligibility. The medical monitor will confirm the content of the eligibility form, and if there is any doubt regarding the subject's eligibility, he/she will consult with the investigator or subinvestigator to determine the subject's eligibility before the baseline examination.

The investigator or subinvestigator will investigate subject background and other information as follows and record it in the source document and CRF.

- Date of visit
- Date of informed consent by the subject (or their legally acceptable representatives) and caregivers
- Subject background information
 - Sex, date of birth, race, ethnicity, and trial country
 - Possibility of getting pregnant in women of childbearing potential (WOCBP) (see Section 5.5 Pregnancy) (if there is no childbearing potential, record the reason)
 - Diagnosis of dementia of the Alzheimer's type (diagnostic criteria of DSM-5 and NINCDS-ADRDA)
 - Timepoint of onset of dementia of the Alzheimer's type
 - Timepoint of diagnosis of dementia of the Alzheimer's type
 - Timepoint of onset of agitation associated with dementia of the Alzheimer's type
 - Complications
 - Medical history (for the 2 years preceding informed consent; however, medical history related to the inclusion/exclusion criteria is not limited to the preceding 2 years.)
 - Medical care category (inpatient or outpatient; if outpatient, institutionalized or care at home)
 - Classification of the main caregiver specified at the start of the trial (hospital staff, care facility staff, family, or other), care status over the 2 weeks prior to the visit (amount of care time per day and days of care in a week)
 - Prior medications and therapies

• Confirmation of eligibility

3.8.1.2 Day of Baseline Examination

To confirm that the subject meets the inclusion criteria and does not fall under the exclusion criteria before starting IMP administration, the investigator or subinvestigator will perform the observations, tests, and assessments shown in Table 3.8-1 and the investigation of the following items and record the results.

- Date of visit
- Confirmation of eligibility

3.8.1.3 Randomization

The investigator or subinvestigator will select subjects who meet the inclusion criteria and do not fall under the exclusion criteria on the basis of the results of the screening examination and baseline evaluation. For the clinical laboratory test and 12-lead ECG, the subject's eligibility will be judged on the basis of the results obtained by the central laboratory and central ECG laboratory at the time of screening.

The investigator or subinvestigator will enter information on eligible subjects in the IWRS. Subjects whose registration was confirmed in the IWRS will be randomized to the brexpiprazole 1 mg, brexpiprazole 2 mg, or placebo group using a dynamic randomization method to minimize bias between the treatment groups regarding the following background factors. The date of randomization and randomization number will be recorded in the CRF.

- Medical care category (inpatient or outpatient^a)
- Prior use of antipsychotics^b (yes or no)
- CMAI total score ($\geq 56 \text{ or } < 56$) in the baseline evaluation

^aSubjects who are institutionalized or receiving care at home and visit the trial site as outpatients

^bReceiving antipsychotics in the 6 months prior to the day of baseline evaluation will be considered as "yes."

The investigator or subinvestigator will provide the IMP and subject diary needed for the period up until the next assessment on the basis of the drug number assigned to the subject in the IWRS and give instructions to bring unused IMPs and the completed subject diary to the next assessment.

3.8.1.4 Seven Days After Administration (Week 1, Day 8) to Seventy Days After Administration (Week 10, Day 71)

The investigator or subinvestigator will perform the observations, tests, and assessments shown in Table 3.8-1 and record the results and date of visit.

At visits where blood is collected for measurement of plasma drug concentrations, the date and time of last IMP administration will be recorded.

At visits from 7 days after administration (Week 1, Day 8) until 56 days after administration (Week 8, Day 57), the investigator or subinvestigator will provide the IMP and subject diary needed up until the next assessment on the basis of the drug number assigned to the subject in IWRS and give instructions to bring unused IMPs and the completed subject diary to the next assessment.

3.8.1.5 Examination at Discontinuation

At discontinuation, the investigator or subinvestigator will perform the observations, tests, and assessments shown in Table 3.8-1 as promptly as possible, within the same day if possible, after discontinuation has been decided and will record the results along with the date of visit. If at time of discontinuation, the subject or caregiver refuses any of the tests or if the investigator or subinvestigator judges that tests cannot be performed due to an emergency, only those observations, tests, and assessments that are feasible will be performed.

3.8.1.6 Follow-up Observation (Twenty-eight Days After Completion or Discontinuation of IMP Administration)

The investigator or subinvestigator will perform the observations, tests, and assessments shown in Table 3.8-1 and record the results and date of visit. These observations, tests, and assessments will also be performed in discontinued subjects unless the subject or caregiver refuses any of the tests or the investigator or subinvestigator judges that tests cannot be performed due to an emergency. Follow-up observation will not be performed for subjects who have transitioned to the extension trial and commenced IMP administration.

3.8.2 Efficacy Assessments

The rater for each of the assessment items should refer to Section 3.8.9 Raters. The results and the date and time of assessments should be recorded in the source documents and the CRF. The schedule for each of the assessment items is shown in Table 3.8-1.

3.8.2.1 Cohen-Mansfield Agitation Inventory

The rater will use CMAI to determine how often each of the 29 agitated behaviors associated with dementia of the Alzheimer's type occurred with each behavior rated on a 7-point scale of frequency through an interview with the caregiver. The evaluation will be made on the basis of information on the subject from 14 days before each assessment day and the frequency of agitation will be evaluated on the basis of the information contained in the subject diary. However, records in the subject diary are supplementary data for assessment, and the investigator or subinvestigator will perform the final assessment based not only on the information contained in the subject diary but also the information collected through an interview with the caregiver.

[29 agitated behaviors]

"Pace, aimless wandering," "inappropriate dressing or disrobing," "spitting (include at meal)," "cursing or verbal aggression," "constant unwarranted request for attention or help," "repetitive sentences or questions," "hitting (including self), " "kicking," "grabbing onto people," "pushing," "throwing things," "strange noises (weird laughter or crying)," "screaming," "biting," "scratching," "trying to get to a different place (e.g., out of the room, building)," "intentional falling," "complaining," "negativism," "eating/drinking inappropriate substances," "hurt self or other (cigarette, hot water, etc.)," "handling things inappropriately," "hiding things," "hoarding things," "tearing things or destroying property," "performing repetitious mannerisms," "making verbal sexual advances," "making physical sexual advances," and "general restlessness"

3.8.2.2 Clinical Global Impression–Severity of Illness

The rater will assess (by time point evaluation) the severity of agitation associated with dementia of the Alzheimer's type on an 8-point scale using the CGI-S.

3.8.2.3 Clinical Global Impression–Global Improvement

The rater will assess (by time point evaluation in comparison with the date of baseline evaluation) improvement of agitation associated with dementia of the Alzheimer's type on an 8-point scale using the CGI-I.

3.8.2.4

3.8.3 Safety Assessments

Evaluation points for each item are shown in Table 3.8-1.

3.8.3.1 Adverse Events

Refer to Section 5 Reporting of Adverse Events.

3.8.3.2 Clinical Laboratory Assessments

In this trial, the clinical laboratory tests shown in Table 3.8.3.2-1 will be conducted by central analysis. Blood and urine samples will be collected from each subject, and the date and time of blood sampling, the date of urine sampling, and the verification of whether blood sampling was performed when the subject was in a fasted state (having fasted for at least 8 hours) will be recorded in the source documents and the CRF. Subject eligibility will be verified using the clinical laboratory test values determined at the central laboratory. For appropriate procedures for the collection, handling, and shipment

of samples, the separately prepared procedures should be followed. The total amount of blood to be collected for clinical laboratory tests during the trial period will be described in the ICF and explanatory materials.

The central laboratory will report the results of tests to the investigator or subinvestigator. The investigator or subinvestigator will confirm the results of tests and date and sign the clinical laboratory test report to make it an official document. The results of laboratory tests, which will be reported directly from the central laboratory to the sponsor as an electronic file, do not need to be recorded in the source documents or the CRF.

Table 3.8.3.2-1Clinical Laboratory Assessments							
Hematology:	Serum chemistry:						
Red blood cell count	ALT						
White blood cell count	AST						
Differential count of white blood cells (neutrophils,	Alkaline phosphatase (ALP)						
eosinophils, basophils, monocytes, and lymphocytes)	Lactic dehydrogenase (LDH)						
Platelet count	Gamma-glutamyl transpeptidase (γ-GTP)						
Hemoglobin	Total protein						
Hematocrit	Total bilirubin						
Prothrombin time (PT)	Albumin						
PT (international normalized ratio [INR])	Cholesterol (total cholesterol, low-density						
Activated partial thromboplastin time (APTT)	lipoprotein [LDL] cholesterol, and high-density						
	lipoprotein [HDL] cholesterol)						
Urinalysis:	Triglycerides						
pH	Blood urea nitrogen (BUN)						
Protein	Creatinine						
Glucose	Uric acid						
Occult blood	СРК						
Urobilinogen	Blood electrolytes (Na, K, Cl, Mg, Ca, P,)						
Specific gravity	Blood glucose (fasting or nonfasting)						
Ketone body	HbA1c (NGSP value)						
	Folate ^a						
	Vitamin B ₁₂ ^a						
	Endocrinology:						
	Serum prolactin						
	Insulin						
	FT4 ^a						
	TSH ^a						
	Immunology						
	HBsAg ^a						
	HCV Ab ^a						

^aPerformed only at screening

3.8.3.3 Physical Examination

The investigator or subinvestigator will conduct a physical examination for HEENT (head, eye, ear, nose, and throat), chest, abdomen, urogenital organs, extremities, nerves, and skin/mucosa.

In the screening examination, all the physical findings obtained on the evaluation day and up to the observation day will be recorded in the source document and CRF. From the baseline evaluation, only information on whether an observation occurred or not and date and time of observation will be recorded in the source document and CRF. Clinically significant physical findings obtained in and after the baseline evaluation will be recorded as AEs in the source document and CRF.

3.8.3.4 Vital Signs (Blood Pressure and Pulse Rate)

After the subject has been rested, the investigator or subinvestigator will measure vital signs in accordance with the methods specified by the trial site. In the screening examination, SBP, DBP, and pulse rate will be measured in the order of supine, sitting, and standing positions. The results, date and time of measurement will be recorded in the source document and CRF. Blood pressure and pulse rate will be measured in the order of supine, sitting, and standing positions after maintaining each position for at least 3 minutes. From the baseline evaluation, blood pressure and pulse rate will be measured in a sitting position. If the subject complained of symptoms of orthostatic hypotension before evaluation in or after the baseline evaluation, measurement should be performed in the supine and sitting positions in so far as possible in the order of the supine, sitting, and standing positions in the same manner as the screening examination.

3.8.3.5 Height and Body Weight

Height and body weight will be measured using a standard measurement method (no shoes, with clothes on).

The date and results of measurements will be recorded in the source document and CRF (body weight in increments of 0.1 kg, height in increments of 0.1 cm).

3.8.3.6 Twelve-lead Electrocardiography

After the subject has been placed in a resting position, the subject's ECG will be recorded using a 12-lead electrocardiograph supplied by the central ECG laboratory. At screening, the subject's eligibility will be assessed based on consecutive triplicate ECG measurements (central reading) obtained during screening. ECG examination will be performed at appropriate intervals after the subject's resting state is confirmed. The third

measurement can be omitted if neither the first nor second measurement (central reading) meets the exclusion criteria (\geq 450 ms for men, \geq 470 ms for women).

The investigator or subinvestigator will check the ECG and assess whether the result is normal or abnormal and will record the date and time of ECG, normal/abnormal judgment, and abnormal findings in the source documents and the CRF. The original of the 12-lead ECG chart will be kept in the medical record or the investigator's file. The central ECG laboratory will collect 12-lead ECG data and measure the heart rate, PR interval, RR interval, QRS interval, QT interval, and QT corrected for heart rate (QTc) $[QTcB = QT interval/(RR interval)^{1/2}, QTcF = QT interval/(RR interval)^{1/3}]$, and the physician of the central ECG laboratory will assess the data.

The central ECG laboratory will report the results of analysis to the investigator or subinvestigator. The investigator or subinvestigator will confirm the results of analysis and date and sign the analysis result report to make it an official document. The investigator or subinvestigator will reconfirm the normal/abnormal judgment with reference to the analysis result report sent from the central ECG laboratory. As the results of analysis by the central ECG laboratory are reported directly from the central ECG laboratory to the sponsor as an electronic file, they do not need to be recorded in the source documents or the CRF.

3.8.3.7 Pregnancy Test

A urine pregnancy test will be performed in WOCBP (see Section 5.5 Pregnancy), and the date of urine sampling and the result of the test will be recorded in the source documents and the CRF. The result of the pregnancy test performed at screening must be obtained before starting IMP administration. If the urine test is positive, another pregnancy test will be performed using serum, and the date of blood sampling will be recorded in the source documents and the CRF. A serum pregnancy test will be performed by the central laboratory selected by the sponsor. For appropriate procedures for the collection, handling, and shipment of samples, separately documented procedures will be prepared and provided prior to the start of the trial. The central laboratory will report the results of tests to the investigator or subinvestigator. The investigator or subinvestigator will confirm the results of tests and date and sign the clinical laboratory test report to make it an official document. The results of serum tests, which will be reported directly from the central laboratory to the sponsor as an electronic file, do not need to be recorded in the source documents or the CRF.

55

3.8.3.8 Other Safety Assessments

The investigator or subinvestigator will record the results and the date and time of the assessments in the source documents and the CRF. The schedule for each of the assessment items is shown in Table 3.8-1.

3.8.3.8.1 Drug-induced Extrapyramidal Symptoms Scale

By using DIEPSS, the investigator or subinvestigator will assess 9 items related to extrapyramidal symptoms on a 5-point scale on the basis of the subject's information from the previous assessment (baseline assessment will be based on the subject's information from the initial screening examination).

Nine items related to extrapyramidal symptoms:

Gait, bradykinesia, sialorrhea, muscle rigidity, tremor, akathisia, dystonia, dyskinesia, and overall severity

3.8.3.8.2 Abnormal Involuntary Movement Scale

By using AIMS, the investigator or subinvestigator will assess the severity of abnormal involuntary movement at 7 sites and 3 global judgment items on a 5-point scale and assess the dental status items "current problems with teeth and/or dentures" and "Dose patient wear dentures" as either "yes" or "no" (assessment at specified time points).

Seven sites:

"Muscles of facial expression," "lips and perioral area," "jaw," "tongue," "upper (arms, wrists, hands, fingers)," "lower (legs, knees, ankles, toes)," and "neck, shoulders, hips"

3.8.3.8.3 Barnes Akathisia Rating Scale

By using BARS, the investigator or subinvestigator will assess the "objective," "subjective—awareness of restlessness," and "subjective—distress related to restlessness" for akathisia on a 4-point scale and a "global clinical assessment of akathisia" on a 6-point scale.

3.8.3.8.4 Sheehan Suicidality Tracking Scale

By using S-STS, the investigator or subinvestigator will assess suicidal attempt and behavior on the basis of 22 question items. At screening, assessment will cover the period spanning the previous 6 months, and for subsequent visits, the assessment will cover the period since the previous visit.

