3.2 Trial Treatments

3.2.1 Dosing and Regimen

The IMP will be administered orally as one tablet once a day for 10 weeks. The doses of brexpiprazole for each group is shown in Table 3.2.1-1. Although the temporal relationship between IMP administration and meals will not be considered, subjects should take the IMP at the specified time in so far as possible. Dose reduction is not allowed during the trial, and if there are tolerability issues, administration of the IMP will be discontinued.

Table 3.2.1-1Doses	ble 3.2.1-1 Doses of IMPs				
Group	Day 1–7	Day 8–14	Day 15–70		
Brexpiprazole 2 mg	0.5 mg	1 mg	2 mg		
Brexpiprazole 1 mg	0.5 mg	1 mg	1 mg		
Placebo	0 mg	0 mg	0 mg		

The dose will be increased to 1 mg after evaluation at Week 1 (Day 8) and to 2 mg after evaluation at Week 2 (Day 15)

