^gBlood pressure and pulse rate will be measured in the order of supine, sitting, and standing positions.

^hEligibility will be assessed based on consecutive triplicate ECG measurements (central reading). The third measurement can be omitted if neither the first nor second measurement (central reading) meets the exclusion criteria.

- ¹Pregnancy test (HCG test) will be performed for WOCBP only. If urinary test is positive, serum test will be performed.
- ^JBlood sampling will be performed before IMP administration if the IMP is administered in Week 10 but does not need to be performed at the time of discontinuation.
- ^kIf blood sampling is not performed for any other test item or for some reason cannot be performed at the time of baseline evaluation, or if blood resampling is necessary, blood sampling will be performed during the trial period.

^lOptional

^mIf for some reason it is not possible to perform blood sampling at this time or if blood resampling is necessary, blood sampling will be performed during the trial period.

Table 3.8-2Allowable Time Windows for Evaluations, Tests, and Observations						
Test Point		Base Date	Allowable Time Window From the Base Date			
Screening period		At the start of screening	Day -42 to Day -2			
Baseline evaluation date		Day 1	Day -1 or Day 1			
Week 1		Day 8	Day 6 to Day 10			
Week 2		Day 15	Day 13 to Day 17			
Week 4		Day 29	Day 27 to Day 31			
Week 6		Day 43	Day 40 to Day 46			
Week 8		Day 57	Day 54 to Day 60			
Week 10		Day 71	Day 68 to Day 78			
Follow-up period ^a		28 days after the final administration of IMP	23 to 35 days after the final administration of IMP			

^aFollow-up observation will not be performed for subjects who have transitioned to the extension trial and commenced IMP administration.

The date of starting IMP administration is designated as Day 1.

All baseline observations, tests, and evaluations will be performed on the day before the start of IMP administration (Day -1) and the day of starting IMP administration (Day 1). CMAI, CGI-S,

, and must be performed on the same day.

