5.2 Eliciting and Reporting Adverse Events

The investigator or subinvestigator will periodically assess subjects for the occurrence of AEs. To avoid bias in eliciting AEs, subjects should be asked the non-leading question: "How have you felt since your last visit?" All AEs (serious and nonserious) reported by the subject must be recorded in the source documents and CRFs provided by the sponsor. The event name, date and time of onset, date and time of recovery, seriousness, severity, causal relationship to IMP, actions taken regarding IMP administration, and outcome thereof will be recorded in the CRF. The period for AE and SAE collection is defined as the period from after a subject has signed the ICF to the date of trial completion.

Use medical terminology in AE reporting. Adverse events should be reported as a single unifying diagnosis whenever possible or, in the absence of a unifying diagnosis, as individual signs or symptoms. Exacerbation or disease progression should be reported as an AE only if there are unusual or severe clinical features that were not present, or experienced earlier, or not expected on the basis of the course of the condition.

Worsening of severity and seriousness of reported AEs must be reported as new AEs in the CRF.

In addition, the sponsor must be notified immediately by e-mail of any IREs according to the procedure outlined below, in Section 5.3 Immediately Reportable Events. Special attention should be paid to recording hospitalization and concomitant medications.

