9.7.3 Sheehan Suicidality Tracking Scale

For the score for each S-STS item (2 through 14), total score, suicidal ideation subscale score, and suicidal behavior subscale score, descriptive statistics of actual measurements and changes from baseline at each time point and the last assessment time point will be calculated for each treatment group and for the overall brexpiprazole group.

In addition, analysis will be performed by the ANCOVA model with treatment group, medical care category (hospitalized or outpatient), and prior use of antipsychotics (yes or no) as factors and baseline as a covariate. Least square means of each treatment group and differences in least square means between each brexpiprazole group and the placebo group, as well as the two-sided 95% CIs will be determined.

10 Pharmacokinetic Analyses

Pharmacokinetic analysis will be performed on the pharmacokinetic analysis set.

Descriptive statistics of plasma brexpiprazole concentrations at time points (0-6, 6-12, 12-18, 18-24, 24-30 hours and > 30 hours) after the most recent dosing as well as trough brexpiprazole concentrations (20-28 hours after the most recent dosing) and plasma brexpiprazole concentrations at all time points will be calculated by treatment group. The descriptive statistics will also be calculated by CYP2D6 phenotype (EM, IM, PM, and Unknown) in each treatment group in the same manner.

The mean plasma brexpiprazole concentration over time will be plotted by treatment group. Plotted diagrams by CYP2D6 phenotype in each treatment group will also be provided in the same manner.

Scatter plots of plasma brexpiprazole concentrations will be provided by treatment group. Scatter plots by CYP2D6 phenotype in each treatment group will also be provided in the same manner.

Plasma brexpiprazole concentrations below the lower limit of quantitation will be handled as 0 (ng/mL) when their descriptive statistics are calculated and when plotted diagrams and scatter plots are created.

11 Pharmacodynamic Analyses

Not applicable.

12 Pharmacogenomic Analyses

CYP2D6 genotype (phenotype) will be tabulated as specified in Section 7.2. CYP2D6 phenotype will also be summarized in subgroup efficacy and safety analyses.

13 Analysis of Other Endpoints

Analysis of other endpoints will be performed using the safety analysis set. Baseline is defined as the last data obtained prior to initiation of IMP treatment.

- ADCS-ADL
- MMSE
- EQ-5D-5L

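### The S-STS look-back is tied to the previous visit, but S-STS is not rated at every visit; read literally, its ratings cover 28 of 70 treatment days

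*Protocol*

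**What the plan says.** Protocol Section 3.8.3.8.4 gives the S-STS a recall period of six months at screening; after that, "for subsequent visits, the assessment will cover the period since the previous visit". The timing comes from elsewhere: Section 3.8.3.8 states that "The schedule for each of the assessment items is shown in Table 3.8-1". That table marks S-STS at screening, baseline (Day 1), Week 4 (Day 29) and Week 10 (Day 71) or discontinuation. It also has visits at Week 1 (Day 8), Week 2 (Day 15), Week 6 (Day 43) and Week 8 (Day 57), with no S-STS at any of them.

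The neighbouring DIEPSS section (3.8.3.8.1) words its look-back differently: the rating is made "on the basis of the subject's information from the previous assessment".

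SAP Section 3.5.8 derives an S-STS total score and ideation and behavior subscale scores. SAP Section 9.7.3 plans "descriptive statistics of actual measurements and changes from baseline at each time point and the last assessment time point" for item, total and subscale scores, and an ANCOVA by treatment group.

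**The concern.** A recall-based scale can be interpreted only if the period asked about is known and is the same for every rater. Here the schedule skips visits and the look-back rule refers to visits. A rater who applies the sentence as written asks at Week 4 about the time since Week 2, and at Week 10 about the time since Week 8. A rater who takes it to mean the last S-STS asks about two or three times as long a period.

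Investigating safety is a stated objective (Section 2.4), and S-STS is a listed safety endpoint (Section 3.6.4) with its own derived scores and model. If the literal rule was followed, the scores say nothing about most of the treatment period. If practice was mixed, scores at one time point come from recall periods of different length.

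**Working it through.** **Inputs**
- Visits, Table 3.8-1: Days 1, 8, 15, 29, 43, 57, 71.
- S-STS ratings from baseline on, same table: Days 1, 29, 71 (completers).
- Visit windows, Table 3.8-2: Week 2, Day 13 to 17; Week 4, "Day 27 to Day 31"; Week 8, Day 54 to 60; Week 10, Day 68 to 78.
- Treatment length, Section 3.2.1: "The IMP will be administered orally as one tablet once a day for 10 weeks".

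The documents give no figure for S-STS coverage. The one figure to reproduce is the treatment length: 71 − 1 = 70 days = 10 × 7.

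**Literal rule (since the previous scheduled visit)**
- Week 4 rating: 29 − 15 = 14 days.
- Week 10 rating: 71 − 57 = 14 days.
- Covered: 14 + 14 = 28 of 70 days (40%).
- Not covered: (15 − 1) + (57 − 29) = 14 + 28 = 42 of 70 days (60%).

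**Range over the allowed windows.** Gap = (Week 2 day − 1) + (Week 8 day − Week 4 day).
- Smallest: (13 − 1) + (54 − 31) = 12 + 23 = 35 days. With Week 10 at its latest, 35 / (78 − 1) = 45% of the time from Day 1 to Week 10.
- Largest: (17 − 1) + (60 − 27) = 16 + 33 = 49 days. With Week 10 at its earliest, 49 / (68 − 1) = 73%.

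**Alternative rule (since the previous S-STS rating)**
- Week 4 rating: 29 − 1 = 28 days.
- Week 10 rating: 71 − 29 = 42 days.
- Covered: 28 + 42 = 70 of 70 days; gap 0.

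**Where the dose steps fall.** Under Section 3.2.1 the dose goes to 1 mg after the Day 8 evaluation and, in the 2 mg group, to 2 mg after the Day 15 evaluation. The first uncovered stretch therefore holds the start of treatment and the step to 1 mg. The step to 2 mg comes after the Week 2 visit, so it lies inside the Week 4 look-back even under the literal rule.

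**Early discontinuation.** S-STS is also rated at discontinuation. The same choice arises there: back to the last visit of any kind, or back to the last S-STS.

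**The case against.** The best counter-argument is that the sentence explains itself. It stands in the S-STS section, and its subsequent visits can only be visits at which S-STS is rated. If *previous visit* has the same referent, Week 4 looks back to Day 1, Week 10 looks back to Day 29, and nothing is missed. The DIEPSS contrast is also weak evidence: DIEPSS is rated at every treatment visit, so during treatment the previous assessment and the previous visit coincide. The protocol is a translation, and the difference in nouns may be no more than that. S-STS raters are trained for the trial (Section 3.8.9), and the training may have settled the matter.

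This reading is plausible, but the text does not establish it. Sections 3.2.2 and 3.8.1.4 call attendances without S-STS visits. Where the protocol fixes a recall period for other scales, it does so without ambiguity: 14 days for CMAI (3.8.2.1) and 28 days for ADCS-ADL (3.8.5.1). The S-STS worksheet and training material are not among the documents, so the anchor actually used cannot be determined from them.

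The objection is right about several stronger conclusions that a reader might draw:
- *Both dose increases go unexamined.* They do not; the step to 2 mg is inside the covered window.
- *Suicidality is unmonitored for 42 days.* Adverse events are recorded from consent to trial completion (Section 5.2), and suicide-related events are an adverse event of interest (SAP 9.2.1) whose term list in SAP Appendix 4 includes suicidal ideation. Elicitation is open, in that "subjects should be asked the non-leading question", and the population has an MMSE of 1 to 22. It is therefore no substitute for structured items, but the period is not unobserved.
- *About 60% of episodes are missed.* This would need episodes that are brief and evenly spread over time. The documents support neither, and ideation that persists into a window would be picked up.
- *A zero at Week 4 will be reported as no suicidality since baseline.* SAP 9.7.3 summarizes by time point and defines no cumulative measure.

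**Conclusion.** The look-back rule is ambiguous, and its literal form does not fit the schedule. Followed literally, it leaves 42 of 70 treatment days (35 to 49 days over the allowed windows) outside any S-STS window in completers. On the other plausible reading the gap is zero. The point that holds without choosing between them is that one sentence permits a 14-day or a 28-day window at Week 4, and a 14-day or a 42-day window at Week 10.

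The day counts assume attendance at every scheduled visit, and for the 42-day figure at the nominal days. A reader might infer that sites did in fact use different windows; the documents show only that they could have.

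The effect is confined to the S-STS scores. The primary and secondary efficacy endpoints and adverse event collection are untouched. Since raters are blinded, there is no evident reason for the choice of window to depend on treatment group. The likely harm is loss of sensitivity and unclear meaning of the scores, not a biased comparison. The point is worth correcting because the correction is small.

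**What to change.** Reword the sentence in Section 3.8.3.8.4 so that, after screening, each rating covers the time since the previous S-STS assessment: baseline since screening, Week 4 since baseline, and Week 10 or discontinuation since the last S-STS. Bring the worksheet and rater training into line. For data already collected, confirm from those materials which anchor was used and state it wherever S-STS results are reported; if practice differed between raters, say so.

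The cost is one sentence and a rater memo, with no added visit, form or procedure. The downside is longer recall: 28 days at Week 4 and 42 days at Week 10, instead of 14 at each under the literal rule. The two on-treatment windows would then differ in length, which should be noted when scores are compared across time points. Comparisons between groups at the same time point would share a common nominal window.
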